4.7.3 Steering Committee and Adjudication

The Steering Committee (SC) for the study will consist of [name], [name], [name], [name], and [name] (principal trial statistician). The Steering committee will be responsible for performing adjudication review and approving any sub-projects, as outlined below.

Review of the following study events will require review from the members of the study steering committee:

1. Death of a patient
2. Surgical complications requiring reoperation

The review, comment, and voting process will occur on REDCAP. Three steering members will need to evaluate each event that is put up for review. The steering committee members are responsible for providing the following inputs for each event:

1. Comments/opinions/justifications
2. Vote (yes or no): question varies depending on the event
 - a. Death event: question not applicable
 - b. Surgical complications requiring reoperation: does the patient need a reoperation?
3. Vote (yes or no): is this event a primary outcome of the study?

Adjudication review will be conducted every 2 months.

Additionally, the steering committee will meet monthly to review standardized REDCap data quality reports.

5.0 STATISTICAL PLAN

5.1 Preliminary Sample size determination:

This study seeks to explore if local antibiotics are effective in reducing infection. Existing literature estimates the rate of infection after intramedullary nailing for open-tibia fracture at 6-21%, with higher rates seen in developing countries^{23,24}. Based on the previous randomized controlled trial conducted at MOI, the rate of deep infection in patients with open tibia fractures who do not receive local antibiotics during operative management was estimated to be 12%. For a relative risk reduction of 50% in the rate of deep surgical site infections, with an alpha (two-sided) of 0.05 and power of 0.80, the estimated sample size was 712 patients (356 per group). Assuming a loss to follow-up of 20%, the final sample size needed was determined to be 890 patients. Given the anticipated enrollment of 15 participants per month, enrollment would take approximately 5 years for a single center study. The study described herein is a pilot trial with a 1-year enrollment period to include 100 patients, approximately 10-20% of the necessary sample size for the definitive trial.

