2.0 STUDY AIMS AND HYPOTHESES

The study described herein is a single-center pilot trial to evaluate the feasibility of necessary protocols including, recruitment, retention, masking and concealment, intervention, and follow-up. The described pilot study will establish effect sizes for appropriate power calculations for a subsequent definitive trial.

The overarching objective of the definitive trial is to test whether injection of intraoperative local gentamicin impacts the rate of fracture-related infection following GA Type I, II or IIIA open tibia fractures in Tanzania. We hypothesize that the risk of fracture-related infection will be reduced by the intraoperative use of locally administered gentamicin at the time of wound closure.

2.1 Definitive Trial Specific Aims:

1. Compare the rate of fracture-related infection at one year after intraoperative local gentamicin injection or intraoperative local saline injection among adults treated operatively for GA Type I, II, or IIIA open tibia fractures. [Primary aim]
2. Compare the occurrence of 1) nonunion, and 2) unplanned fracture-related reoperation after intraoperative local gentamicin injection or intraoperative local saline injection among adults treated operatively for GA Type I, II, or IIIA open tibia fractures. [Secondary aims]
3. Evaluate the economic impact of fracture-related infection (FRI) after open tibia fractures in Sub-Saharan Africa including direct medical costs and lost productivity. [Secondary aims]

Null hypothesis: There is no difference in the rate of fracture-related infection between local gentamicin administration and saline administration for adult patients with GA Type I, II, or IIIA open tibia fractures treated in Sub-Saharan Africa.

Alternative hypothesis: Intraoperative local gentamicin administration decreases the occurrence of fracture-related infection in adult patients with GA Type I, II, or IIIA open tibia fractures treated in Sub-Saharan Africa.

2.2 Feasibility Trial Specific Aims:

Outcomes include rates of screening, enrollment, randomization, allocation, reliability of intervention, subject retention, and data completeness.

Specifically, feasibility outcomes are:

1. Recruitment: number of patients screened, number and proportion of patients screened that are eligible, enrolled, randomized, and receive intervention.

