4.7 Outcome Measures

4.7.1 Feasibility Trial Outcomes

7. Recruitment: number of patients screened, number and proportion of patients screened that are eligible, enrolled, randomized, and receive intervention.
8. Retention: number and proportion of randomized patients who attend each follow-up visit. We aim for an adherence rate at follow-up of 80% at one year, which was achieved in our previous open tibia fracture trial performed through the same collaborative partnership.
9. Data collection completeness: proportion of fracture-related infection criteria, EuroQol-5 Dimensions, 3-level questionnaire (EQ-5D), Function Index for Trauma (FIX-IT), and

Modified Radiographic Union Score for Tibia (mRUST)¹⁷ indices complete at each time-point.

10. Solution quality control: confirmation of the ongoing sensitivity of standard organisms to trial solutions via interval testing. This will occur once per month for the first 6 months and once every 6 months thereafter by the Muhimbili University of Health and Allied Sciences (MUHAS) microbiology lab, with results evaluated by unmasked study personnel.
11. Masking and concealment: determination of the continued masking of surgeons to solution identity via intraoperative surgeon survey.
12. Evaluation of primary and secondary outcomes: reliability of fracture-related infection and mRUST scoring, validation of telephone criteria for fracture-related infection, radiographic image quality, and completeness of EQ-5D and FIX-IT.

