5.2 Statistical Methods

Feasibility outcomes described in 4.7.1 will be summarized using means and proportions, without the use of inferential statistics. Given the principle feasibility aim of this pilot trial, the following statistical methods are described primarily for planning purposes. Statistical methodology to be performed in the analysis of each primary, secondary, and subsidiary outcome is outlined below. The statistical analysis plan (SAP) will provide additional detail on statistical analysis and will be modified as necessary based on data collected in this pilot trial.

Outcomes Analysis Planned for Definitive Trial

Outcome	Data	Method of analysis
---------	------	--------------------

Primary		
Rate of fracture-related infection	FRI criteria	Relative Hazard as estimated by two-sided binomial regression with the complementary log-log link, with a type I error rate (alpha) of 0.05.
Secondary		
Rate of unplanned reoperation	Review of complications	Fisher's exact test on the 2×2 cross-tabulation
Rate of nonunion	Nonunion criteria	
Subsidiary		
Quality of Life	EQ-5D	
Inflammatory Markers	CRP	
Radiographic Healing	mRUST	
Clinical Healing	FIX-IT	
Direct costs	TM Analysis	
Indirect costs	WPAI	
FRI Suggestive Criteria	FRI criteria	Fisher's exact test on the 2×2 cross-tabulation

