7.5 Dissemination Policy

At the conclusion of the study there will be a principal manuscript reporting the findings of the feasibility trial primary study endpoints. This data will be used to inform the definitive trial.

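### Does giving the pilot a year to enrol 100 patients undercut the 15 per month assumed for the definitive trial?

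*Combined protocol and SAP*

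**What the plan says.** Section 5.1 (Preliminary Sample size determination) derives 712 evaluable patients for the definitive trial and raises this to 890 for 20% loss to follow-up. It then gives a duration: "Given the anticipated enrollment of 15 participants per month, enrollment would take approximately 5 years for a single center study". The pilot follows directly: "The study described herein is a pilot trial with a 1-year enrollment period to include 100 patients". The Study Summary gives the same size as 50 per arm, and section 4.1 names one hospital.

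Section 2.2 introduces the feasibility outcomes this way: "Outcomes include rates of screening, enrollment, randomization, allocation, reliability of intervention, subject retention, and data completeness". The numbered recruitment outcome, there and in section 4.7.1, reads "number of patients screened, number and proportion of patients screened that are eligible, enrolled, randomized, and receive intervention". Retention carries a numerical aim in section 4.7.1: "We aim for an adherence rate at follow-up of 80% at one year". On analysis, section 5.2 says: "Feasibility outcomes described in 4.7.1 will be summarized using means and proportions, without the use of inferential statistics". On the use of the results, section 7.5 (Dissemination Policy) says: "This data will be used to inform the definitive trial".

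**The concern.** Two adjacent sentences about one hospital appear to imply different speeds. A centre that randomises 15 patients a month should not need a year to reach 100, and over a year it would reach 180. The documents give no start-up allowance, no statement that the year is an upper limit, and no source for the 15.

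The recruitment outcome seems to make this worse. Its numbered wording lists counts and proportions of those screened, none of them per unit of calendar time, and it sets no target. A high proportion enrolled is compatible with slow accrual. Retention has an 80% aim, so a reader could conclude that the assumption behind the 5-year estimate goes untested in a trial run to assess feasibility. What is at stake is whether one centre could complete the definitive trial in about 5 years or would need nearly 9, which bears on the number of sites.

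**Working it through.** **Inputs, all from section 5.1:** control risk 12%; relative reduction 50%, so 6% on gentamicin; two-sided alpha 0.05; power 0.80; loss 20%; 15 participants per month; pilot of 100 in one year. Allocation is 1:1 (section 4.5).

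**Step 1. Reproduce the plan's figures.** The usual two-proportion formula with pooled variance under the null and no continuity correction is

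n per arm = [1.960 × √(2 × 0.09 × 0.91) + 0.842 × √(0.12 × 0.88 + 0.06 × 0.94)]² / 0.06² = 356 after rounding up.

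- Total: 2 × 356 = 712, as stated.
- Allowing for loss: 712 / (1 − 0.20) = 890, as stated.
- Duration: 890 / 15 = 59.3 months = 4.9 years, which agrees with about 5 years.
- Pilot share: 100 / 890 = 11.2% and 100 / 712 = 14.0%, both inside the stated 10-20%.

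Nothing is miscalculated.

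**Step 2. Compare the pilot with the 15 per month.**

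- Time to 100 at 15 per month: 100 / 15 = 6.7 months (95% range 5.4 to 8.0 under constant Poisson accrual).
- Yield of a full year at 15 per month: 15 × 12 = 180.
- Rate if the year is used in full: 100 / 12 = 8.3 per month, or 8.33 / 15 = 56% of the anticipated rate.

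**Step 3. Ask what the 8.3 is.** A target of 100 within 12 months is met at any rate r with 100 / r ≤ 12, that is r ≥ 8.3. The figure is a lower bound. A rate of 15 meets it, so the two sentences can both be true.

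**Step 4. Size the consequence if accrual is slower.** Time to 890 at one centre is 890 / r:

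| Rate per month | Months | Years |
|---|---|---|
| 15 | 59.3 | 4.9 |
| 12 | 74.2 | 6.2 |
| 10 | 89.0 | 7.4 |
| 8.3 | 106.8 | 8.9 |

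**Step 5. Check whether the pilot as written would reveal a slower rate.** The rate needs the number randomised and the months open to enrolment. The first is a listed outcome. The second is basic trial information, and randomisation runs through REDCap (section 4.5). Mean randomisations per month is also a mean, so it fits the descriptive summary in section 5.2. The precision is adequate: 100 patients in 12 months would give an exact Poisson 95% interval of 6.8 to 10.1 per month, well below 15. At a true 15 per month the pilot would fill in roughly 5.4 to 8.0 months. The two situations are easy to tell apart.

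**Step 6. Trace where the 15 is used.** It appears only in the duration sentence. It does not enter 712, 890, the power, the alpha or any analysis in section 5.2.

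**The case for a change.** The best case for a change is that the plan does not commit itself to the comparison that matters. Finishing the pilot on time would not confirm 15 per month, because any rate from 8.3 upward does that. The introductory line in section 2.2 speaks of rates, but the numbered outcome turns these into counts and proportions. Retention has an aim matching the 20% loss assumed in the sample size, and the accrual assumption has no counterpart. Since the pilot exists to judge feasibility, one extra descriptive statistic would cost almost nothing.

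Part of this stands. The gap between 6.7 and 12 months is unexplained, the 15 has no stated source, and no explicit comparison with it is promised. The rest is weaker. Retention is the only one of the six feasibility outcomes with a numerical target, so recruitment is treated like most of the others. Retention also bears directly on the required sample size, through the step from 712 to 890, and the accrual rate does not. The year for 100 patients can itself be read as an implicit recruitment goal. The interval that excludes 15 presupposes a full-year pilot, so it shows precision under that scenario and is no evidence against the 15. Writing a range of about 5 to 9 years into section 5.1 would present a rate derived by the reader as one the sponsor expects.

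**Conclusion.** No change follows. The two statements in section 5.1 are unreconciled but not contradictory: one is an anticipated rate, the other a fixed number within a window that implies at least 8.3 per month. The calculations are correct, and nothing in the documents shows the 15 or the 5-year estimate to be wrong.

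What is missing is explanatory detail that an analyst supplies without difficulty. Number randomised over months open gives the rate, and the pilot's results are already committed to planning the definitive trial. If accrual proves slower, the duration changes as in the table, up to 8.9 years at 8.3 per month. No estimate, test or conclusion of the pilot changes. This rests on constant accrual at a single centre and, for the 8.9 years only, on the pilot taking its full 12 months.

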5.2 Statistical Methods

Feasibility outcomes described in 4.7.1 will be summarized using means and proportions, without the use of inferential statistics. Given the principle feasibility aim of this pilot trial, the following statistical methods are described primarily for planning purposes. Statistical methodology to be performed in the analysis of each primary, secondary, and subsidiary outcome is outlined below. The statistical analysis plan (SAP) will provide additional detail on statistical analysis and will be modified as necessary based on data collected in this pilot trial.

Outcomes Analysis Planned for Definitive Trial

Outcome	Data	Method of analysis
---------	------	--------------------

Primary		
Rate of fracture-related infection	FRI criteria	Relative Hazard as estimated by two-sided binomial regression with the complementary log-log link, with a type I error rate (alpha) of 0.05.
Secondary		
Rate of unplanned reoperation	Review of complications	Fisher's exact test on the 2×2 cross-tabulation
Rate of nonunion	Nonunion criteria	
Subsidiary		
Quality of Life	EQ-5D	
Inflammatory Markers	CRP	
Radiographic Healing	mRUST	
Clinical Healing	FIX-IT	
Direct costs	TM Analysis	
Indirect costs	WPAI	
FRI Suggestive Criteria	FRI criteria	Fisher's exact test on the 2×2 cross-tabulation

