4.6.4 Radiographs

Orthogonal images will be obtained and digitally copied using screen capture. Images will then be uploaded into REDCap. Radiographs are then sent for review by the adjudication committee, and are assessed for radiographic signs of healing using the mRUST score by two fellowship-trained orthopaedic trauma surgeons. In cases of disagreement between reviewers, decisions are made by consensus.

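### Reliability of FRI and mRUST scoring is a pilot outcome, but the rule in Section 5.2 leads to no chance-corrected agreement statistic and no interval

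*Combined protocol and SAP*

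**What the plan says.** Section 4.7.1 (Feasibility Trial Outcomes), item 12, includes "reliability of fracture-related infection and mRUST scoring, validation of telephone criteria for fracture-related infection"; Section 2.2, item 6, also lists scoring reliability. Section 5.2 sets one method for all outcomes in that list: "Feasibility outcomes described in 4.7.1 will be summarized using means and proportions, without the use of inferential statistics". The table of methods in Section 5.2 covers only the definitive trial. No section names a kappa, an ICC or any other agreement statistic, or sets a reliability target. Section 5.2 does add that "The statistical analysis plan (SAP) will provide additional detail on statistical analysis", but the text supplied contains none on this point.

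The ratings come from two sources:

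- **mRUST (Section 4.6.4).** Two trauma surgeons score the radiographs. "In cases of disagreement between reviewers, decisions are made by consensus".
- **FRI (Section 4.7.3).** Three steering committee members vote in REDCap on each event put up for review, including a yes/no vote on whether it is a primary outcome. The events listed are deaths and complications leading to reoperation. The Study Summary describes adjudication more broadly, but no section says that every participant's FRI status is rated by more than one person.

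**The concern.** Reliability is a question about whether raters agree on the same patient. A mean per reader does not answer it, and a raw percentage answers it poorly when one category is rare, because raters who mostly record no infection will agree most of the time whatever their skill. FRI is the primary outcome of the definitive trial. An mRUST of 10 or less is part of the nonunion definition, a secondary outcome. The pilot is meant to inform both. A reassuring percentage could leave a scoring problem unnoticed. Without an interval, readers could not see how little a pilot of 100 patients can establish about reliability.

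**Working it through.** **Inputs.** Section 5.1 gives the infection rate in patients "who do not receive local antibiotics during operative management was estimated to be 12" per cent. The planned effect halves that rate, and the test is two-sided at the 5% level with 80% power. The gentamicin rate is therefore 0.5 × 12% = 6%. Section 5.1 also cites a literature range of 6–21%. Allocation is 1:1, so the pooled rate under the planning assumptions is (12% + 6%)/2 = 9%. The plan does not state this 9%.

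**Reproducing the plan's figure.** The two-proportion formula with pooled variance and no continuity correction gives

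n = [1.96·√(2 × 0.09 × 0.91) + 0.842·√(0.12 × 0.88 + 0.06 × 0.94)]² / 0.06² = 356 per group.

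The total is 712, and 712/0.80 = 890. All three match Section 5.1, so the 12% and 6% are read correctly.

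**Chance agreement and kappa for FRI.** Take two independent raters who each call a proportion p positive:

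- chance agreement Pe = p² + (1 − p)²
- kappa = (Po − Pe)/(1 − Pe), where Po is raw agreement

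At 9%, Pe = 0.0081 + 0.8281 = 0.836. With Po = 0.90, kappa = 0.0638/0.1638 = 0.39.

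| FRI rate in the rated set | Chance agreement | Kappa at 90% raw | Kappa at 95% raw |
|---|---|---|---|
| 6% | 88.7% | 0.11 | 0.56 |
| 9% | 83.6% | 0.39 | 0.69 |
| 12% | 78.9% | 0.53 | 0.76 |
| 21% | 66.8% | 0.70 | 0.85 |

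These rows apply if all participants are double-rated. In a set made up of deaths and reoperations the FRI share is not stated, and it is probably higher because reoperations for infection are among the events. At assumed shares of 30% and 50%, 90% raw agreement gives kappa of 0.76 and 0.80.

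**What a proportion can show.** At 9% and 90% raw agreement, each rater calls 9% positive and 10% of patients are discordant, so 9% − 5% = 4% are positive for both. Positive agreement is 2 × 0.04/(0.09 + 0.09) = 44%. Negative agreement is 2 × 0.86/(0.91 + 0.91) = 95%.

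**Precision.** In a simulation of 100 double-rated patients at 9%, true kappas of 0.4, 0.6 and 0.8 gave expected raw agreement of 90%, 93% and 97%. The 95% sampling ranges of the estimated kappa were 0.06–0.68, 0.26–0.85 and 0.52–1.00. A few points of raw agreement separate weak from good reliability, and kappa is itself imprecise with about nine events.

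**mRUST.** The chance calculation above does not carry over to an ordinal scale from 4 to 16. The problem is different. If one reader scores higher on half the patients and lower by the same amount on the rest, the two means are equal although the readers disagree on every patient.

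**The case against.** The strongest reply has five parts.

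- **Section 5.2 does not shut out good statistics.** A reader might infer that it permits percent agreement and nothing else. It does not go that far. Positive and negative agreement are proportions, and the 44% above would expose the weakness. The mean absolute difference between readers is a mean. A kappa point estimate is descriptive. Only the confidence interval arguably conflicts with the bar on inference. This stands: suitable statistics are unnamed, and the stated rule does not lead to them.
- **The 9% may not apply.** A reader might take 83.6% as the chance agreement this pilot will face. The documents do not support that, because only deaths and reoperations go to three voters. This stands, and the figures are conditional.
- **The coefficient matters.** AC1 at 9% and 90% raw agreement is (0.90 − 0.164)/(1 − 0.164) = 0.88, against a kappa of 0.39. This stands. It is a reason to report positive and negative agreement beside kappa, and not to treat AC1 as interchangeable with it.
- **Consensus need not erase readings.** Resolving a disagreement implies that separate readings came first, and nothing says they are overwritten. This stands in part: nothing says they are kept, either.
- **It is a pilot, and more SAP detail is promised.** That leaves room for the repair but does not supply it. Reliability is a named pilot outcome, and individual readings have to be kept while the pilot runs.

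**Conclusion.** The gap is real and modest. A named feasibility outcome is tied to a summary rule that does not suit it and gives no interval.

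For FRI, the same 90% raw agreement would correspond to a kappa anywhere from about 0.11 to 0.70 across the plan's own 6–21% range. This assumes two independent raters with equal marginal rates and every participant double-rated. The 9% case also assumes the planned 50% reduction and that the deep-infection rate carries over to the FRI definition. On the adjudicated events the distortion is probably smaller, by an amount the documents do not allow one to calculate. For mRUST there is no comparable figure. The point there is that means do not measure agreement and that retention of separate readings is unstated.

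A reader might infer that the pilot would pass poor scoring as reliable and so dilute the definitive trial's effect. The documents do not support that as a prediction. They set no reliability threshold or progression rule for a raw percentage to satisfy, they give no rater error rates, and the FRI criteria are specific clinical or laboratory findings.

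**What to change.** 1. In Section 5.2, exempt the reliability part of item 12 from the sentence on means and proportions. The completeness elements of that item can stay under it.
2. State that each reader's mRUST score is stored before consensus, and that each voter's primary-outcome vote is retained in REDCap.
3. For mRUST, report an ICC or weighted kappa from the two existing readers, with a 95% confidence interval.
4. For FRI, report a multi-rater kappa together with positive and negative agreement on the adjudicated events, each with a 95% confidence interval.
5. State which patients the FRI figure covers. Agreement on deaths and reoperations says nothing about infections diagnosed in clinic without reoperation.

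The cost is SAP wording, some data entry and a little analysis. Intervals will be wide because FRI events are few, and the report should say so. Rating every participant's FRI status in duplicate would need rater time that the plan does not provide, so it should not be added unless raters are already available.
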